6.4. DERIVED TIMEPOINTS

For subjects in the AGS-16C3F group, each infusion date starts a new cycle. Cycles are numbered consecutively. For subjects in the axitinib group, clinic visits and most other events are identified by the planned study day.

The following derived visit definitions will apply to tables, figures, and listings unless otherwise specified for a particular analysis:

- **Worst Post-Baseline:** The worst value collected in the period from C1D1 post-dose through the later of the safety follow-up visit or the last dose date + 28 days (inclusive).
- **Safety Follow-Up:** Everyone is required to have an actual safety follow up visit and one measurement for the safety f/u. For subjects who don't have a safety F/U visit, report the worst value recorded during the period from the day of last dose or decision to end treatment through the subject's last available assessment.
- **Final Visit:** The chronologically last available assessment.
- **Any Time during Treatment/Safety Follow-up:** From C1D1 post-dose through the later of the safety follow-up visit or the last dose date + 28 days (inclusive).

Eye assessments are identified in the raw data only by the exam date. Data from the AGS-16C3F subjects will be assigned to a Cycle based on comparing the exam date to the infusion dates. Data from the axitinib subjects will be assigned to a scheduled assessment or identified as a PRN exam, based on the calculated study day of the exam (see Section 6.6, Visit Windowing Conventions).

For tables that show eye-related safety results by timepoint during the study, data from the AGS-16C3F subjects will be grouped for analysis as follows: Day 43 will include data recorded from post-dose C1D1 through Predose C3D1, inclusive; Day 106 will include data recorded from Post-dose C3D1 through Predose C6D1, inclusive; subsequent intervals will be defined similarly at 3-cycle intervals during treatment. For the axitinib subjects, the analysis periods are based on the scheduled/PRN classifications that have been assigned. For both groups, assessments that are made after the end of treatment (EOT) will be grouped together as "EOT and beyond". Both planned and PRN eye assessment data will be included in all intervals.

It may be necessary to derive other timepoint records for some analyses. Where applicable, these are specified for each analysis that requires them.

6.5. RETESTS, UNSCHEDULED VISITS AND EARLY TERMINATION DATA

In general, data recorded at the nominal visit will be presented for by-visit summaries (if applicable). Unscheduled measurements will not be included in by-visit summaries unless otherwise specified for a particular analysis, but will contribute to the End of Cycle, End of Treatment, or End of Study value, or best/ worst case value where required (e.g. shift table).

In the case of a retest (same visit number assigned), the latest available measurement for that visit will be selected for analyses (if applicable). ECGs will be recorded in triplicate; these are not "retest" values. Handling of the ECG data is addressed in Section 19.4.

Early termination data will be mapped to the next available visit number for by-visit summaries.

Listings will include scheduled, unscheduled, retest and early discontinuation data.

6.6. VISIT WINDOWING CONVENTIONS

Subjects in both treatment arms will have disease assessments every 8 weeks (± 7 days), counting from first dose or first infusion, irrespective of any treatment delay. The Schedule of Assessments (Protocol Section V) provides additional information about the procedures and assessments that are to be completed during each visit or Cycle.

The EDC-specified visit designations, and/or Cycle and Cycle Day designations for AGS-16C3F subjects, will be used for listings and for any summaries by visit or timepoint.

If visit windowing is determined to be required for any analysis, the upper limit of each analysis window will be the protocol-specified upper limit of the “acceptable” window for each assessment. The lower limit of the next consecutive window will be set to the following day. Within each window, the assessment closest to the target day and time will be selected for analysis, unless otherwise specified. Other assessments within the window will be treated as unscheduled or PRN assessments. This strategy will help to keep the results aligned with any event-based presentations that may be produced.

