#### **5.1.3.1 Prophylactic Steroid Eye Drop Use (AGS-16C3F Subjects Only)**

Subjects randomized to AGS-16C3F must use 1% prednisolone acetate ophthalmic suspension prophylactically (prophylaxis steroid drops) starting from Day (-1) of each treatment cycle. Prophylaxis steroid drops will be applied to both eyes, 1 drop to each eye, 6 times daily while awake for the first 7 days of each cycle (starting at Day [-1]), then 4 times daily while awake for an additional 7 days, and then stopped. This will be repeated in each treatment cycle. Refer to [Table 5](#) below.

Should the subsequent dose be delayed, the “no prophylaxis steroid eye drop use” period will extend. The study will not provide the prophylaxis steroid drops (i.e., each site to supply); but the cost will be reimbursed.

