#### **7.4.1 Analysis of Primary Endpoint**

##### **7.4.1.1 Primary Analysis**

The primary efficacy endpoint is progression-free survival (PFS), defined as the time from the date of randomization to the earliest of documented disease progression as defined by RECIST v 1.1 per investigator radiology review, or death from any cause. Disease assessment will continue until disease progression, even after the originally assigned treatment is discontinued.

The primary analysis of investigator assessed PFS will be performed in accordance with the ITT principle in the FAS. All subjects who undergo randomization will be included in the primary analysis and grouped according to the treatment groups assigned by randomization.

For the primary analysis of PFS, the difference in treatment effect between treatment groups will be tested using the stratified log rank test (on ECOG Performance Status and the number of prior systemic RCC regimens) at a one-sided 0.1 significance level.

Estimation of the hazard ratio for treatment and its corresponding one-sided 90% CI will be determined using a stratified Cox proportional hazards model (on ECOG Performance Status and the number of prior systemic RCC regimens), without any other covariate. A two-sided 95% CI will also be reported in the clinical study report. Homogeneity in the hazard ratios between strata will be examined by Wald's test. The corresponding results without stratification will be reported as supplemental analyses. The adequacy of the model will be evaluated, including an assessment of the proportional hazards assumption (Therneau, 2000).

For the primary analysis, PFS will be right-censored for subjects who meet one or more of the following conditions:

- Subjects with no post-baseline disease assessments unless death occurred prior to the first planned assessment (in which case death will be considered a PFS event)

- Subjects who initiate subsequent anti-cancer therapy or intervention in the absence of documented progression
- Subjects who die or have disease progression after missing 2 or more consecutively scheduled disease assessment visits
- Subjects who are last known to be alive and progression-free on or before the data cut-off date

For such subjects, PFS will be right-censored according to the conventions described in [Table 13](#). These conventions are based on the May 2007 FDA Guidance for Industry “Clinical Trial Endpoints for the Approval of Cancer Drugs and Biologics”.

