3.4. ASSIGNMENT AND ALLOCATION TO TREATMENT

Randomization will be performed via Interactive Response Technology (IRT). After the subject has completed screening and been deemed eligible, the site staff will access the study's IRT system for subject randomization ≤5 days before C1D1. The IRT system will not allow randomization to occur if it has been more than 28 days since the main ICF has been signed. Specific procedures for randomization through the IRT are described in the study's IRT manual.

Subjects will be randomized at 1:1 ratio to either AGS-16C3F or axitinib. Randomization will be stratified according to ECOG Performance Status (0 or 1), RCC histology (clear cell or non-clear cell), and the number of prior systemic RCC regimens (2 for clear cell or 1 for non-clear cell, >2 for clear cell or >1 for non-clear cell).

The RCC histology categorization is defined as the following:

- Clear cell group:
 - Clear cell
 - Clear cell component
 - Mixed clear cell
- Non-clear cell group:
 - Papillary and everything else (e.g., chromophobe, collecting duct, renal medullary, etc., not so common but possible other RCC histologies)

Table B. Categories for Stratification of Prior Systemic RCC for Randomization Process

Prior Systemic RCC Regimen Stratum	Clear Cell Subjects	Non-Clear Cell Subjects
2	2 prior systemic RCC regimens	1 prior systemic RCC regimen
>2	>2 prior systemic RCC regimens	>1 prior systemic RCC regimens

Per protocol, subjects are expected to start study treatment ≤5 days after randomization.

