3.5. SAMPLE SIZE JUSTIFICATION

For subjects with metastatic RCC who have progressed after at least 2 prior lines of therapy, a median PFS of 4 months is anticipated for the control agent. It is hypothesized that AGS-16C3F will improve median PFS in such subjects by 2 months (i.e., 4 vs 6 months). Under the assumption of exponential distribution of PFS, such an improvement corresponds to a hypothesized hazard ratio of 0.667. If this hypothesized hazard ratio is true, 110 PFS events provide 80% power to achieve a one-sided p-value of 0.1 or smaller. Such a result will be achieved when the observed hazard ratio is 0.783 or smaller; and the observed difference in median PFS is 1.1 months or larger (assuming observed median PFS for the control arm is 4 months). Assuming accrual of approximately 7 subjects per month for 18 months, 110 PFS events are projected 24 months after the date the first subject is randomized. Approximately 134 subjects may be enrolled to accommodate for up to 10% of subjects who may become lost to follow-up.

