17.1.2.3. PFS Censoring Rules (Set 3)

The PFS Censoring Rules (Set 3) are based on Table B (PFS 2 – uniform progressions and assessment dates) of the May 2007 FDA Guidance for Industry “Clinical Trial Endpoints for the Approval of Cancer Drugs and Biologics”. Set 3 rules are designed to correct for potential bias due to any differences in the follow-up schedules for disease assessments, including unscheduled visits. These alternative censoring rules will be used for sensitivity analyses of the PFS.

Under Set 3 rules, an observed PFS event is defined as documented disease progression or death due to any cause. The occurrence of a PFS event will be imputed to the date of the scheduled disease assessment time. Accordingly, the dates of observed events will be adjusted as follows:

- If disease progression is documented between 2 scheduled disease assessments, the planned date of the later scheduled assessment will be assigned as the date of progression.
- In the event of death, the date of the endpoint will not be adjusted.

- If the response at a scheduled time (X) is classified as Indeterminate (IND) or Not Assessed (NA) and at the next scheduled timepoint (X+1) the best response is PD, then the planned date of the first timepoint (X) will be used as the uncensored date of progression.
- Censoring will be similar to Set 1, except that the planned dates of scheduled assessments will be used for the censored values.

Table G summarizes the handling of missing data and PFS determination under the Censoring Rules (Set 3).

Table G. PFS Censoring Rules (Set 3): Uniform Progression and Assessment Dates

Situation	Date of Progression or Censoring	Outcome
Death before first scheduled disease assessment	Actual date of death	Progressed
Death or documented disease progression at a scheduled disease assessment	Actual date of death or planned date of the scheduled disease assessment, whichever occurs first	Progressed
Death or documented disease progression between scheduled disease assessments	Actual date of death or planned date of next subsequent scheduled disease assessment after the documented disease progression, whichever occurs first	Progressed
A disease assessment of “indeterminate” or “not assessed” at Visit X, followed by documented disease progression at Visit X+1	Planned date of scheduled disease assessment at Visit X	Progressed

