17.1.3. PRIMARY ANALYSIS OF PRIMARY EFFICACY VARIABLE

The primary objective of this study is to test the hypothesis that PFS is superior (longer) for subjects treated with AGS-16C3F than for subjects treated with axitinib.

The primary analysis of PFS based on the investigator's assessment of disease will be performed in accordance with the ITT principle in the FAS. All subjects who undergo randomization will be included in the primary analysis and grouped according to the treatment groups assigned by randomization. The Censoring Rules (Set 1) which are presented in Section 17.1.2.1 will be used to derive the event status and PFS times.

The difference between treatment groups will be tested using a stratified log rank test at a one-sided 0.1 significance level. The stratification factors will be the ECOG PS and the number of prior systemic RCC regimens, without any other covariate(s). If the direction of the difference between treatment arms favors AGS-16C3F, then the observed significance level (p-value) of the 1-sided test of superiority of AGS-16C3F will be calculated as $0.5 * p$ -value from a two-sided log-rank test (corresponding to a chi-squared test with d.f.=1). If the direction of the difference favors axitinib, then the observed significance level will be calculated as $(1 - (0.5 * p\text{-value from the two-sided log-rank test}))$.

Kaplan-Meier survival curves for the primary analysis variable will be produced, overall and by stratum. The following descriptive statistics will be reported in a table, overall and by stratum:

- Progression status:
 - Number and percent of subjects with observed disease progression per RECIST
 - Number and percent of subjects who died without disease progression beforehand
 - Number and percent of censored subjects
- Number and percent of censored subjects, by reason for censoring
- Estimated progression-free survival time (months), including the minimum, 25th percentile, 50th percentile (median), 75th percentile, and maximum. The 2-sided 95% CIs for the 25th, 50th, and 75th percentiles, calculated using Greenwood's formula for the standard error, will also be reported.

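### PFS is timed from randomization but scans and Set 3 planned dates are counted from first dose, so any between-arm difference in the start lag shifts the one-sided 10% error towards AGS-16C3F, and Set 3 does not correct it

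*SAP*

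**What the plan says.** **Two clocks.** Protocol 7.4.1.1 gives PFS as "defined as the time from the date of randomization to the earliest of documented disease progression" or death, and SAP 17.1.1 repeats it. Disease assessments are every 8 weeks (±7 days) from C1D1 (Protocol 2.2.1 and 5.5). SAP 6.6 describes this as "counting from first dose or first infusion, irrespective of any treatment delay".

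**The gap between them.** Protocol 4.4 and 5.2.5 put randomization no more than 5 days before C1D1. SAP 3.4 says "Per protocol, subjects are expected to start study treatment" within 5 days. The limit is the same in both arms and no minimum is stated.

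**The one arm-specific step.** Under Protocol 5.1.3.1, AGS-16C3F subjects must use 1% prednisolone acetate eye drops "prophylactically (prophylaxis steroid drops) starting from Day (-1) of each treatment cycle". Table 5 shows Day (-1) as the day before Day 1. I found no matching pre-dose step for axitinib.

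**Dating of events.** Set 1, the primary rule, uses the actual scan date (SAP 17.1.2.1, Table E). Set 3 moves events to planned dates. For a progression found between two scheduled scans, "the planned date of the later scheduled assessment will be assigned as the date of progression" (SAP 17.1.2.3). Its stated aim is to correct for bias from differing follow-up schedules.

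**The test.** PFS is "tested using a stratified log rank test at a one-sided 0.1 significance level" (SAP 17.1.3).

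**The concern.** The treatment arm is unknown until randomization. A compliant AGS-16C3F subject therefore starts at least 1 day later, while an axitinib subject may start the same day. With a scan every 56 days, most events in a round fall close together in time. The log-rank test uses only their order. PFS is calculated in days, and the rounding to a tenth of a month is for display (SAP 17.1.1), so one day is enough to untie two events. If AGS-16C3F scans sit a day or more later after randomization, axitinib events come first round after round, and the test drifts towards AGS-16C3F with no true benefit.

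The planned safeguards would not reveal this. Set 3 dates run from C1D1 too, so they keep the lag and remove the scan-date scatter that partly hides it. The compliance table in SAP 16.2 compares scans with that same schedule. I found no planned table of the randomization-to-first-dose lag by arm. At stake is the error rate of the primary test and the reassurance a reader would take from Set 3.

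**Working it through.** **1. Reproduce the plan's figure.** SAP 3.5 says "110 PFS events provide 80% power to achieve a one-sided p-value of 0.1 or smaller", and the assumed medians of 4 and 6 months mean "such an improvement corresponds to a hypothesized hazard ratio of 0.667". With 1:1 allocation:

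- Events = 4(z₀.₉₀ + z₀.₈₀)² / (ln HR)² = 4(1.2816 + 0.8416)² / 0.4055² = 109.7, so 110.
- Critical HR = exp(−1.2816 × 2/√110) = 0.783.

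Both match the SAP. The rejection limit is z ≤ −1.2816.

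**2. The lag difference the rules support.** Suppose lags are spread evenly over the compliant ranges. AGS-16C3F at 1–5 days has mean 3.0; axitinib at 0–5 days has mean 2.5. The difference is 0.5 day. Anything larger is an assumption.

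**3. Hand check of the mechanism at its extreme.** Take a true HR of 1, every axitinib subject starting on day 0, every AGS-16C3F subject on day 1, and scans exactly on schedule.

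- Median 4 months = 121.75 days. The chance of passing a 56-day round is 0.5^(56/121.75) = 0.727, so 27.3% progress.
- Round 1 events per arm: 67 × 0.273 = 18.29.
- Axitinib events come first, with 67 of 134 at risk in AGS-16C3F: expected AGS-16C3F share 18.29 × 67/134 = 9.15.
- AGS-16C3F events follow, with 48.71 axitinib subjects left: 18.29 × 67/115.71 = 10.59.
- Observed minus expected = 18.29 − 9.15 − 10.59 = −1.45. Had the two arms' events been tied, it would be 0.
- Later rounds shrink by the factor 0.727, so the total is about −1.45/(1 − 0.727) = −5.3.
- SD ≈ √(110/4) = 5.24, so z shifts by about −1.0.

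Simulation with 10% of events as exactly dated deaths gives a mean z of −0.936. Then Φ(−1.2816 + 0.936) = 0.365, which matches the simulated 36.5%. Spread in lags and scatter in scan dates dilute this sharply, as the next step shows.

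**4. Simulated one-sided type I error.** From the SAP: 67 per arm, exponential PFS with median 4 months in both arms, cut-off at the 110th event, nominal 10%. Assumed: the lags, the scan scatter, and 10% of events being deaths.

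| Lag in days, AGS-16C3F vs axitinib | Mean difference | Scatter uniform ±7 d | Scatter SD 3 d | Planned dates / no scatter |
|---|---|---|---|---|
| 0 vs 0 | 0 | 10.2% | 9.8% | 10.0% |
| 1–5 vs 0–5 | 0.5 | 11.1% | 11.2% | 12.9% |
| 1–5 vs 0–4 | 1 | 11.8% | 12.8% | 17.2% |
| 2–5 vs 0–3 | 2 | 13.2% | 15.8% | 26.1% |
| 3–5 vs 0–2 | 3 | 14.5% | 18.1% | 33.8% |
| 1 vs 0, all subjects | 1 | 11.9% | 12.6% | 36.5% |
| 5 vs 0, all subjects | 5 | 18.6% | 23.7% | 33.1% |

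Rows 1, 2, 6 and 7 use 20,000 trials per cell and a four-stratum log-rank test (Monte Carlo error 0.2–0.3 points). Rows 3–5 use 6,000–8,000 trials (about 0.3–0.5 points). The two scatter columns approximate Set 1; the last approximates Set 3.

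**5. After the change.** With scans counted from randomization, the error is 10.0–10.5% for fixed lag differences of both 1 and 5 days. With scans left as they are and Set 3 dated from randomization by visit number, it is 8.5–9.6%, slightly conservative.

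**The case against.** The strongest reply is that the documents permit a lag difference but do not establish one. Both arms have the same 5-day limit, both need a C1D1 visit with pre-dose procedures, and no expected or actual lag is given by arm. If sites leave the same gap in both arms, the error is about 10%. That stands, and it rules out three stronger readings.

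- *A reader might infer that AGS-16C3F progressions are necessarily dated later and that the 10% level is broken.* The text supports only a difference in the compliant minimum, 1 day against 0. A same-day AGS-16C3F start would breach the eye-drop requirement, but nothing in the randomization or C1D1 sections blocks it. A longer wait for an infusion slot is conjecture.
- *A reader might take an error of about a third as the size of the problem.* That needs events dated exactly on the planned grid, together with arm lags that barely overlap or do not overlap at all. It concerns a sensitivity analysis, not the primary test. Scatter across the permitted ±7 days shrinks the effect considerably.
- *A reader might infer that every randomized subject who is never dosed is censored at randomization.* SAP Table E does this only where there is neither a death nor a post-baseline assessment. A death before the first scheduled assessment is an event.

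Two further replies carry weight. This is a Phase 2 proof-of-concept comparison at a deliberately lenient level. Protocol version 6.0 is dated August 2020, with the study period planned to end in 3Q2020, so re-anchoring scans can affect few of them. Neither reply excuses Set 3, which is offered as the correction for schedule differences and cannot correct this one.

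**Conclusion.** The concern holds in a limited form, at moderate severity; it is not a must-fix. The two clocks differ, the compliant minimum lag is unequal, and any systematically longer AGS-16C3F lag favours AGS-16C3F. The one-sided 10% error is therefore not guaranteed, and the excess depends on a lag that the plan does not report.

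In the case nearest the rules, the primary analysis has an error of about 11%, roughly one point above nominal. Set 3 has about 13%. Errors of about 13–18% on actual dates, or 26–34% on planned dates, require mean lags 2–3 days apart, which is assumed. These sizes rest on exponential PFS with a 4-month median, 10% of events being deaths, and the stated scatter. Independently of the true lag, Set 3 does not remove the offset and can enlarge it, so agreement between Set 1 and Set 3 is no reassurance on this point.

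**What to change.** 1. **SAP 17.1.2.3 (Set 3).** Compute planned dates from randomization by visit number (days 56, 112, 168 and so on), so both arms share the same dates. This works after scans are done and needs only a wording and programming change.
2. **SAP outputs.** Tabulate the randomization-to-first-dose lag by arm and show it beside the Set 1 result, so that a reader can judge which row of the table above applies. This is one table from dates that the planned PFS and exposure derivations already use.
3. **Protocol 2.2.1 and 5.5, and SAP 6.6.** For scans not yet done, count assessments from randomization in both arms. The cost is that the first scan falls up to 5 days earlier relative to first dose, which is inside the existing 7-day window.
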